**Transcranial Photobiomodulation for
reducing autism symptoms in
children.**

October 1, 2020

PROTOCOL TITLE:

Transcranial photobiomodulation for reducing autism symptoms in children.

PRINCIPAL INVESTIGATOR:

Name	[name]
Department	N/A
Phone Number	

CO-INVESTIGATORS:

Name	[name]
Department	N/A
[contact]

Name	[name], CFA, Esq.
Department	N/A
[contact]

1.0 Purpose of the study:

The purpose of this 8-week open label feasibility study is to assess the tolerability, safety and efficacy of Transcranial LED Therapy for language learning and reducing symptoms of autism in children.

The investigators propose to enroll up to 30 participants of both genders ages 24 months to 6 years who have been previously diagnosed with moderate to severe ASD by licensed professionals according to the Diagnostic and Statistical Manual of Mental Disorders, Fifth Edition (DSM-5) criteria for Autism Spectrum Disorder (ASD).

The hypothesis to be tested is that exposure to photobiomodulation and speech parsing program will reduce children's symptoms of autism, such as delays in language production and comprehension, anxiety, tantrums, limited eye-contact and improve responsiveness.

2.0 Background / Literature Review / Rationale for the study:

2.1 Background Science of Photobiomodulation and Rationale:

There are several studies that suggest that mitochondrial energy disturbance is an underlying mechanism of autism, for at least some of the children. Specifically, Weisman, Kelley, Bauman, Cohen, Murray, Mitchell and Kern (2008) looked at the medical records of 25 children diagnosed with autism and found that "Levels of blood lactate, plasma alanine, and serum ALT and/or AST were increased at least once in 76%, 36%, and 52% of patients, respectively". Furthermore, 2 out of those 25 people had rare mtDNA mutations. The authors concluded that at least for a subset of ASD children, mitochondrial disturbances in energy production could be the underlying mechanism. Furthermore, Giulilvi, Zhang, Omanska-Klusek, Ross-Intra, Hertz-Picciotto, Tasson and Pessach (2010), looked at biochemical markers of ASD kids (2-5yo), and concluded that ASD children are more likely to have Mitochondria dysfunction, mtDNA replication and mtDNA deletion than neurotypical ones.

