7.7 On-going Data Collection: Parents will be asked to keep a daily diary of the child's behavior, specifically – words spoken, comprehension of instructions, eye contact, his sleep pattern, number of tantrums, anxiety, social interaction and eating. Qualitative data will be collected through short weekly interviews with the parents. These interviews can take place either in [name] office during the child's treatment or by phone. During those weekly interviews, the parents will be asked questions about their children's responsiveness to language, number of words they can produce, eye-contact, anxiety, frequency of tantrums, eating, and difficulties falling asleep and sleeping through the night. Please see attached proposed script for the weekly call. The qualitative data will be used to further inform and supplement quantitative data (total CARS 2 scores).

The study will collect qualitative and quantitative data. The quantitative data will be the total CARS2 scores of the participants of both Control and Treatment groups, obtained before and after the study is done. Mixed Design Analysis of Variance will be used to analyze quantitative data. **In addition, we will collect Before and After Prefrontal cortex EEG from the control and experimental treatment groups to measure electrophysiological changes in Prefrontal cortex. after treatment. EEG data will be analyzed (using Time-Frequency analysis), and after baseline normalization, the data will be used in aggregate to compare conditions numerically. The between group comparison before the treatment will be conducted using between subject T-test for each brainwave . The between group comparison will be conducted after treatment for each brain wave using between subject t-test. In addition, for the treatment condition only Before and After comparison will be conducted, using within subject t-test.** In addition, we will obtain qualitative data from weekly parental interviews, during which we will ask participants' parents about their children's behavior (see attached protocol). Qualitative data will be used for information purposes and will supplement quantitative data.

7.8 Blinding of the Researcher: [name] (the PI) will not be present in the room when the child is receiving the treatment. She will not be aware what group each particular participant has been placed in. [name] will be conducting the pre and post-testing interviews, as well as the on-going weekly interviews with the parents.

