9.0 Recommendation for Only One Parent Consent

Both this proposed study and the investigational device do not involve greater than minimal risk.

Rationale for the device:

Safety of Photobiomodulation: Photobiomodulation has been extensively studied on humans for more than 30 years, including its use for neurological conditions. There are several photobiomodulation products (for neurological conditions) that are on currently on the market (using both LED and Lasers). The consumers report no side-effects.

After more than three decades of research there are no known major side effects attached to photobiomodulation therapy.

Rare Minor Side effects for first time users only include: Tiredness (temporary) – probably due to the release of metabolites but the majority report a resurgence of energy. Headaches (temporary) – from the reactivation of neural connections and increased microcirculation.

Safety Issues of our product specifically: Our product emits non-laser based irradiation (incoherent light) with a low level energy intensity. Infrared emits non-laser based irradiation (incoherent light) with a low level energy intensity. We use 850 nm. The participants might perceive slight warm. No other perceptions will be produced by wearing the device. No feelings of discomfort are anticipated (the device is especially made for children, it's very comfortable and soothing to wear). There are no known side-effects of photobiomodulation (with 30 years of research and studies, including research on 5 year old children diagnosed with ASD).

Rationale for the study:

The study activities include: 1) wearing the device and / or 2) Listening to the audio program which provides language acquisition input or 3) free play while listening to nursery rhymes. In addition, the parents will be interviewed about the child's behavior on a weekly basis.

None of these activities present greater than minimal risk to the health and well-being of the participants.

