The child may feel uncomfortable wearing the headband and may want to take it off early	
• If the child wants to take off the headband, we will first encourage him to wear it, by attempting to divert his attention to other things,

	
such as toys and music.
 
 • If, however, the child insists on taking off the headband, he / she will not be forced to wear it and he / she may be able to take it off before the conclusion of the session.

Breach of confidentiality (child's data being seen by someone who shouldn't have access to it)
	
 • We'll keep all children identifying information separate from the research data, but we'll be able to link it by using a study ID. We will destroy this link after we finish collecting and analyzing the data.

If child is in the group that receives placebo (no active treatment), the child's symptoms or condition may not improve and the parent will be upset
	
 • We are conducting the study to see the effects of photobiomodulation on young children diagnosed with ASD.

		
If the effect is beneficial, the device may be available for treatment in the future and the particular child and other children may benefit from the outcome.
			

 
  
The child maybe receiving concomitant medical treatment
 	 
 • Even though there are the tPBM with any medication currently receiving on a regular basis, will be excluded from participating in this pilot study. This will be determined during initial screening. 	
 
 	 
 • 	
 
	
The child maybe receiving concomitant medical treatment
	
 • Even though there are the tPBM with any medication currently receiving on a regular basis, will be excluded from participating in this pilot study. This will be determined during initial screening. 		
 • 	
 • Even though there are no interaction of the tPBM with any medications, children currently receiving any medications on a regular basis, will be excluded from participating in this pilot-study. This will be determined during initial screening.

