	
interaction is extremely unlikely. The positive interaction (e.g., children becoming more responsive to ABA therapy) will also be monitored and recorded in parental diaries. The children should be able to receive their regular behavioral therapies while being enrolled in this study.

There may be risks that we do not know about yet. Exposure to LED lights is not known to have any negative side effects.
	
 • When the child will wear the headband, the child will be exposed to LED lights. The lights will be both red and near infra red. The lights will range in frequency

	
from 660 MHz to 850 MHz.
 
 • After years of study, there are no known negative side effects of photobiomodulation. • Throughout the study, we'll tell parents if we learn anything that might affect their decision to let their child participate.

Some participants may have to be withdrawn from the study
	
 • If the child is not able to attend all the required sessions and the caregiver is not able to reschedule a cancelled session within a 3 day window, then the child will have to be withdrawn from the study. • If the child becomes aggressive or self-injurious

	
during the session, then the child will have to be withdrawn from the study.
 
 • In that event, only the data that has been collected up to the date of withdrawal will be kept. • All identifying information will not be shared and all reports will be aggregated. • We will ask the child's parents for permission to contact them in the future with follow up questions regarding the child's behavior.

Furthermore, the study will be under oversight of [name], who is a board-certified pediatric psychiatrist with more than 10 years of experience working with children with ASD
	

14.0 Provisions to Protect the Privacy and Confidentiality of Participants and the Research Data:

Participants will be only interacting with [name] or [name], Esq. Participants and their parents will be tested individually, in a quiet room, and their confidentiality will be protected, as they won't be interacting with each other or with anybody else outside of the researchers.

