We will conduct weekly interviews with the parents, asking them questions about child's behavior and functioning to collect both safety and efficacy data. The interviews will be conducted either by telephone or in person (per parental choice). Please attached interview protocol. [name], a licensed clinical psychologist will review the data. The detailed qualitative data will be collected. No statistical analysis is necessary.

If a participant shows sudden developmental regress, we will recommend immediate neurological evaluation and his/her participation will be discontinued (unless this participant has been manifesting regress prior the start of the study). If two participants suddenly manifests signs of regress (not anticipated, not seen before in prior photobiomodulation studies), we will immediately discontinue the study.

16.0 Data, and if applicable, Specimen Banking:

The raw research data will be stored for 6 years. The identifying parental information will be kept for a year, for potential follow up interviews. The consent form will include their permission to keep identifying data for a year.

Although we do not plan to re-contact the participants after the study is complete, a follow up interview in 6 months or a year could be useful to assess the sustainability of the benefits of photobiomodulation. In this case, we will be applying for a separate IRB (minimal risks) to conduct the follow up interview. Presently, we do not plan to do it (although we recognize that it could potentially be useful for research purposes).

The data will be stored in encrypted, password protected files in a secure cloud.

17.0 Data Sharing:

Only aggregated data will be shared with scientific community (via publications). Only aggregated data will be shared with potential investors. If individual data (e.g., from an interview) is shared for illustrative purposes, identifying information will NOT be shared (STUDY ID will be assigned to each participant).

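### The diary and interview topics that Section 15.0 relies on for safety data list no item on headache, daytime tiredness or warmth, the effects that Section 9.0 itself anticipates

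*Protocol*

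**What the plan says.** Protocol Section 1.0 states that the study is to "assess the tolerability, safety and efficacy of Transcranial LED Therapy", with tolerability and safety named ahead of efficacy.

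Section 9.0 describes what may be felt. It has "Rare Minor Side effects for first time users only include: Tiredness (temporary" and then "Headaches (temporary) – from the reactivation of neural connections and increased microcirculation". It adds that the device may be perceived as slightly warm. The same section later says "There are no known side-effects of photobiomodulation", and the Section 13.0 risk table says "Exposure to LED lights is not known to have any negative side effects".

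Section 15.0 describes the weekly parent interview as "asking them questions about child's behavior and functioning to collect both safety and efficacy data". Section 7.7 lists what the interview covers: response to language, and then "number of words they can produce, eye-contact, anxiety, frequency of tantrums, eating, and difficulties falling asleep and sleeping through the night". The daily diary has eight topics: speech, understanding, eye contact, sleep, tantrums, anxiety, social contact and eating. Sections 7.7 and 15.0 both refer to an attached script or interview protocol, which is not part of the text supplied.

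Under Section 7.8, as it reads with names removed, one blinded person does the pre- and post-testing and the weekly interviews. A different researcher is in the room during treatment and does no CARS testing, interviewing or analysis.

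**The concern.** The protocol says which effects it expects, and then describes a safety instrument whose listed topics do not include them. What is found depends on what is asked, more so here than usual. Section 10.0 describes these children, aged 2 to 6, as limited in comprehension and responsiveness, so a headache may never be put into words. It would have to be noticed by a parent and volunteered in an interview about language, behaviour, eating and sleep.

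At stake is the meaning of a clean result. Section 2.2 foresees home use, and Section 2.1 gives the age range in the cited autism study as 5 to 18 years. If few or no reports come in, a reader needs to know whether parents were asked. The inconsistency between Sections 9.0 and 13.0 also matters in its own right, because Section 10.0 has parents told of the possible risks.

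**Working it through.** The plan states no figure on this point, so there is none to reproduce. The check is a comparison of the passages.

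| Effect in 9.0 | How 9.0 classes it | Diary topics (7.7) | Interview topics (7.7) | Risk table (13.0) |
|---|---|---|---|---|
| Tiredness | Rare minor side effect, temporary | No item; sleep pattern is nearest | No item; trouble falling or staying asleep is nearest | Not listed |
| Headache | Rare minor side effect, temporary | No item | No item | Not listed |
| Warmth | Possible perception | No item on warmth or skin | No item on warmth or skin | Not listed |

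Coverage is 0 of 2 for the effects labelled as side effects, and 0 of 3 if warmth is counted. Night-time sleep is related to daytime tiredness but does not record it.

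The following illustration shows why asking matters. Inputs:
- n = 15 children on active light (Section 5.0).
- p = true rate of an effect, assumed to be 10%; the documents give no rate.
- s = share of events that reach the record, assumed to be 1, 0.5, 0.25 or 0; the documents do not give this either.

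Chance of no reports at all: (1 − p·s)^15.
- s = 1: 0.90^15 = 0.206, or 21%
- s = 0.5: 0.95^15 = 0.463, or 46%
- s = 0.25: 0.975^15 = 0.684, or 68%
- s = 0: 100%

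One-sided 95% upper limit for the true rate after 0 reports in 15: (1 − 0.05^(1/15))/s = 0.181/s.
- s = 1: 18%
- s = 0.5: 36%
- s = 0.25: 72%

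With the 16 Active children in the SAP (Primary Outcome), the limit at s = 1 is 1 − 0.05^(1/16) = 17%.

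The 18% is a property of the sample size and would apply under perfect collection. It does not measure the defect. The part due to collection is the widening as s falls. If nobody asks, s is unknown and no limit can be stated.

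**The case against.** The strongest objection is that the script has not been seen. Section 7.7 gives a prose summary of topics, and the attached script may ask about headache, tiredness or any other complaint. This stands. The point is about the protocol text, and the first step is to read the script. The diary list, which is a separate instrument, is silent too.

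Second, the listed topics are not purely about efficacy. Section 15.0 says they serve both purposes, and worse sleep, eating, anxiety or tantrums could be signs of pain or fatigue. Section 13.0 also has staff follow changes in the response to behavioural therapy. This also stands: some events would surface indirectly. But a change in tantrums or appetite is non-specific and would not be recorded as headache.

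Third, discomfort is not ignored. Section 13.0 says "If the child wants to take off the headband, we will first encourage him to wear it", but goes on to say that a child who insists may remove it, and Section 10.0 says a child showing discomfort will not be forced. Sections 6.0 and 7.5 keep the caregiver in the room throughout, so the parent interviewed may have seen what happened. What is missing from the description is a record of it. The data list in Section 14.0 cannot settle that either way: it also omits the EEG and the diary, so it is not exhaustive.

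Fourth, the Section 9.0 statement that no side effects are known can be read as shorthand for an earlier sentence there about major ones. That is plausible, but the text does not say so.

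A reader might infer more than the documents support:
- That the trial will claim to be free of side effects without having asked. No such claim is planned; those phrases describe earlier studies and products.
- That three side effects are named. Section 9.0 labels two and calls warmth a perception.
- That every child is a first-time user. Section 4.0 has no exclusion for earlier photobiomodulation, and Section 9.0 says such products are on the market.

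**Conclusion.** The point holds for the protocol text. The topics listed for the diary and interview include no item on headache, daytime tiredness, or warmth or skin reaction, although Section 9.0 anticipates these effects and Section 15.0 makes the interview the source of safety data. Coverage is 0 of 2 labelled side effects and 0 of 3 with warmth; the sleep topics give indirect coverage of tiredness at most.

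The conclusion is conditional on the unseen weekly script. If the script asks about these effects, what remains is to bring Section 7.7 into line with it and to reconcile Sections 9.0 and 13.0. If it does not, an absence of reports would be weak evidence on tolerability and safety, by an amount that cannot be calculated because the reporting share is unknown. The 36% and 72% limits rest on assumed shares and are only illustrations.

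Nothing here shows that the device causes these effects or that events were missed. The point concerns what is collected, so it does not depend on the SAP, of which only the CARS sections could be read.

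**What to change.** 1. Check the attached weekly script against Section 9.0. If it lacks these effects, add short fixed items to the diary and script on headache or head-holding and on unusual tiredness, plus one open question on any other problem. Use identical wording in both arms and start at session 1, since Section 9.0 ties these effects to first use.

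2. Keep warmth and skin questions out of the weekly interview. The interviewer is the blinded tester and control devices are never lit, so a parent's answer about warmth could reveal the allocation. Have the researcher already in the room record warmth, skin appearance and attempts to remove the device in a session log, asking the caregiver present. Withhold the log from the CARS rater until the final CARS rating is done.

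3. Tabulate all items by arm.

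4. Reconcile the two statements in Section 9.0 with each other and with the Section 13.0 risk table, and check that the consent information agrees. The consent pages were not reviewed, so no mismatch is asserted there.

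5. The SAP already gives post-treatment results. If collection is finished, the report should state which effects were asked about and which were not.

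The cost is a few lines in existing forms, a short amendment and a few minutes per session. More minor events will be reported in both arms. The warmth and skin items must be kept from the blinded rater; a parent may still mention warmth in answer to the open question, and this cannot be fully prevented.

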10.0 Consent Process

Parents of child participants will be debriefed about the purposes of the study. They will be explained risks and benefits. The researcher will answer all their questions. The participants will review the Informed Consent form. Parents will be given an opportunity to ask questions about the consent. The parents will be explained that they do not have any obligation to participate in the study and their refusal to participate will not affect any current treatment or benefits that they or their child currently receives. This explanation will take place in person, in [name] office, in a private room.

During the conversation, we will ask questions to ensure that the parent understands that the participation is voluntary, that the child may be placed in the placebo group, the time commitment required, the possible risks of being in the study and possible benefits.

Prior to enrolling a child in the study, we will collect the signed Informed Consent from the parents of every participant.

We will not be obtaining consent from the child participants. The reason is as follows: children between the ages 2 to 6 years, especially those diagnosed with ASD, have limited mental capacity and cannot be reasonably consulted about the risks and benefits of the study. Children will be asked to wear a device on their head. Due to their limited level of comprehension and responsiveness, they may not be able to give an affirmative verbal assent.

Nonetheless, if children demonstrate a visible discomfort, or verbally say that they do not want to wear the device, they will not be forced to do it.

11.0 Financial Compensation:

No financial compensation will be provided.
Parents of participants will be responsible for the cost of transportation to the research facilities.
This is minimal risk to the participants.

12.0 Potential Benefits to Participants:

The possible benefit for the participant child may be improvement of speech, improvement of responsiveness, reduction of tantrums, reduction of anxiety, improvement of sleep, and improvement of eye contact.

13.0 Risks to Participants:

Potential Risks	Mitigating Factors
Some questions may be very personal or upsetting to the parents	
• Parents may skip any questions that they do not want to answer.
The child may feel uncomfortable wearing the headband and may want to take it off early	
• If the child wants to take off the headband, we will first encourage him to wear it, by attempting to divert his attention to other things,

	
such as toys and music.
 
 • If, however, the child insists on taking off the headband, he / she will not be forced to wear it and he / she may be able to take it off before the conclusion of the session.

Breach of confidentiality (child's data being seen by someone who shouldn't have access to it)
	
 • We'll keep all children identifying information separate from the research data, but we'll be able to link it by using a study ID. We will destroy this link after we finish collecting and analyzing the data.

If child is in the group that receives placebo (no active treatment), the child's symptoms or condition may not improve and the parent will be upset
	
 • We are conducting the study to see the effects of photobiomodulation on young children diagnosed with ASD.

		
If the effect is beneficial, the device may be available for treatment in the future and the particular child and other children may benefit from the outcome.
			

 
  
The child maybe receiving concomitant medical treatment
 	 
 • Even though there are the tPBM with any medication currently receiving on a regular basis, will be excluded from participating in this pilot study. This will be determined during initial screening. 	
 
 	 
 • 	
 
	
The child maybe receiving concomitant medical treatment
	
 • Even though there are the tPBM with any medication currently receiving on a regular basis, will be excluded from participating in this pilot study. This will be determined during initial screening. 		
 • 	
 • Even though there are no interaction of the tPBM with any medications, children currently receiving any medications on a regular basis, will be excluded from participating in this pilot-study. This will be determined during initial screening.

The child maybe receiving concomitant medical treatment
	
 • Even though there are the tPBM with any medication currently receiving on a regular basis, will be excluded from participating in this pilot study. This will be determined during initial screening. 				
	
 • 				

 
  
The child might be receiving behavioral
 	 
 • There are no known interactions with any behavioral treatment with any behavioral treatment. 	
 
	
The child might be receiving behavioral
	
 • There are no known interactions with any behavioral treatment with any behavioral treatment. 	
 • There are no known 		

The child might be receiving behavioral
	
 • There are no known interactions with any behavioral treatment with any behavioral treatment. 				

Intervention such as ABA simultaneously with participating in the study.
	
treatment. [name] and [name] Ph.D will monitor (based on parental interviews and diaries) at the child's progress and if there are any changes (as reported by the parents) in children's ability or willingness to relate to ABA therapists or benefit from ABA therapy, the parents will be offered to withdraw form the study. We think that negative likelihood of such an interaction is extremely unlikely. Positive interaction (e.g., child becoming more responsive to ABA therapy) will also be monitored and recorded in parental diaries. Parental children should be able to receive their regular behavioral therapies while being enrolled in this study.
	
[name] Ph.D will monitor (based on parental interviews and diaries) at the child's progress and if there are any changes (as reported by the parents) in children's ability or willingness to relate to ABA therapists or benefit from ABA therapy, the parents will be offered to withdraw form the study. We think that negative likelihood of such an

		
each child's progress and if there are any changes (as reported by the parents) in children's ability or willingness to relate to ABA therapists or benefit from ABA therapy, the parents will be offered to withdraw form the study. We think that negative likelihood of such an

	
interaction is extremely unlikely. The positive interaction (e.g., children becoming more responsive to ABA therapy) will also be monitored and recorded in parental diaries. The children should be able to receive their regular behavioral therapies while being enrolled in this study.

There may be risks that we do not know about yet. Exposure to LED lights is not known to have any negative side effects.
	
 • When the child will wear the headband, the child will be exposed to LED lights. The lights will be both red and near infra red. The lights will range in frequency

	
from 660 MHz to 850 MHz.
 
 • After years of study, there are no known negative side effects of photobiomodulation. • Throughout the study, we'll tell parents if we learn anything that might affect their decision to let their child participate.

Some participants may have to be withdrawn from the study
	
 • If the child is not able to attend all the required sessions and the caregiver is not able to reschedule a cancelled session within a 3 day window, then the child will have to be withdrawn from the study. • If the child becomes aggressive or self-injurious

	
during the session, then the child will have to be withdrawn from the study.
 
 • In that event, only the data that has been collected up to the date of withdrawal will be kept. • All identifying information will not be shared and all reports will be aggregated. • We will ask the child's parents for permission to contact them in the future with follow up questions regarding the child's behavior.

Furthermore, the study will be under oversight of [name], who is a board-certified pediatric psychiatrist with more than 10 years of experience working with children with ASD
	

14.0 Provisions to Protect the Privacy and Confidentiality of Participants and the Research Data:

Participants will be only interacting with [name] or [name], Esq. Participants and their parents will be tested individually, in a quiet room, and their confidentiality will be protected, as they won't be interacting with each other or with anybody else outside of the researchers.

The participants will be explained that they can refuse to answer any question. They can also refuse to participate in the study at any time. We do not anticipate uncomfortable questions, however, we will assure the participants that their level of comfort is of utmost importance, and we will explain to them that there is no penalty involved for their refusal to answer any specific question.

Only [name] and [name] will be able to access individual information. The participants will be immediately assigned Study ID number and only STUDY ID will be used for data analysis and reporting. Only aggregated data will be used for further reporting to the scientific community or to the business community. Individual data will be reported for illustrative purposes only with STUDY ID (not identifying personal information).

The following information will be included as data: Signed consent form (immediately scanned and stored in a cloud). Pre and Post-test Cars2 scores (with STUDY ID assigned). Weekly interview data (with STUDY ID assigned).

Identifying information will include Name and Age, Gender and number of therapy hours of the participant, Name and phone number of the parent. Children's age, gender and number of therapy hours will be used for matching purposes (for assigning to the control or treatment condition). Neither names of the participants nor names and phone numbers of their parents will be used for data analysis or reporting. Their names and phone numbers will be stored separately, in encrypted (password protected) file, in a secure cloud. Secure clouds as well as encryption and password protection will be used to protect identifying information.

The raw research data will be stored for 6 years. The identifying parental information will be kept for a year, for potential follow up interviews. The consent form will include their permission to keep identifying data for a year.

Although we do not plan to re-contact the participants after the study is complete, a follow up interview in 6 months or a year could be useful to assess the sustainability of the benefits of photobiomodulation. In this case, we will be applying for a separate IRB (minimal risks) to conduct the follow up interview. Presently, we do not plan to do it (although we recognize that it could potentially be useful for research purposes).

The data will be stored in encrypted, password protected files in a secure cloud.

15.0 Data Monitoring Plan to Ensure the Safety of Participants:

We will conduct weekly interviews with the parents, asking them questions about child's behavior and functioning to collect both safety and efficacy data. The interviews will be conducted either by telephone or in person (per parental choice). Please attached interview protocol. [name], a licensed clinical psychologist will review the data. The detailed qualitative data will be collected. No statistical analysis is necessary.

If a participant shows sudden developmental regress, we will recommend immediate neurological evaluation and his/her participation will be discontinued (unless this participant has been manifesting regress prior the start of the study). If two participants suddenly manifests signs of regress (not anticipated, not seen before in prior photobiomodulation studies), we will immediately discontinue the study.

16.0 Data, and if applicable, Specimen Banking:

The raw research data will be stored for 6 years. The identifying parental information will be kept for a year, for potential follow up interviews. The consent form will include their permission to keep identifying data for a year.

Although we do not plan to re-contact the participants after the study is complete, a follow up interview in 6 months or a year could be useful to assess the sustainability of the benefits of photobiomodulation. In this case, we will be applying for a separate IRB (minimal risks) to conduct the follow up interview. Presently, we do not plan to do it (although we recognize that it could potentially be useful for research purposes).

The data will be stored in encrypted, password protected files in a secure cloud.

17.0 Data Sharing:

Only aggregated data will be shared with scientific community (via publications). Only aggregated data will be shared with potential investors. If individual data (e.g., from an interview) is shared for illustrative purposes, identifying information will NOT be shared (STUDY ID will be assigned to each participant).
